9.3. Exploratory Efficacy Analysis

The exploratory efficacy analysis are to evaluate the changes from Baseline (Day 1) as compared to Placebo on the following measurements:

- Evaluate the difference on the autoantibody and complement profiles between the two treatment groups
- Evaluate the differences on the gene expression profiles and the serum protein levels between the two treatment groups.
- Compare the mean improvement (from Baseline to Day 85; or Baseline to Day 169 in CLASI damage scores of those randomized to be treated with RSLV-132 and those randomized to receive placebo.

9.3.1. Autoantibody and Complement Profiles

Serum samples will be analyzed by either a local or central laboratory using validated methods. The analysis will provide values for the following autoantibodies and indicate if the result is positive, negative, or equivocal using the validated assay range for the testing laboratory: Ro-52/60, La, Sm, SmRNP, U1 RNP A/68, dsDNA. The summary of actual values of these tests will also be provided. Complement C3 and C4 values will also be summarized.

Summary of observed values: Observed values, change from baseline and a shift from baseline categories at each scheduled visit of autoantibody profile will be summarized. The percentages will be calculated based on the actual number of subjects at each visit in each treatment group of the FAS. No statistical testing will be performed.

9.3.2. Gene Expression Profiles

Ribonucleic acid (RNA) will be extracted from whole blood to measure the expression level of genes that are related to inflammatory pathways though to be involved in SLE. Samples will be obtained at selected visits during the study from Baseline to the End of Study visit. The analysis of gene expression profiles will be performed elsewhere and will not be a part of this SAP.

9.3.3. Serum Protein Levels

Serum samples will be obtained at various visits during the study to analyze the level of circulating serum proteins. The protein analysis will measure protein levels related to the inflammatory process. The analysis will be carried out using a multiplexed immunoassay. The analysis of serum protein levels will be performed elsewhere and will not be a part of this SAP.

9.3.4. CLASI Damage Score

CLASI Damage assessment will be performed for each subject at scheduled visits to determine the SLE disease activity for each subject at the visit. The assessment includes each anatomical location. The total score of the Damage subsection (defined as the sum of the scores from each anatomical location) will be used in the summary.

Summary of observed values: Observed values of total Damage score and the change from baseline at each scheduled visits will be summarized. No statistical testing will be performed.

10. SAFETY ANALYSES

The safety assessment of the treatment will be compared between the two groups by adverse events and laboratory results as well as any physical findings that have changed from baseline. The safety analysis will include adverse events, concomitant medications, laboratory data, vital signs and immunogenicity of RSLV-132.

All data will be summarized as observed and no data imputation will be performed.

10.1. Adverse Events

Adverse events will be coded using the Medical Dictionary for Regulatory Activities (MedDRA version 19.0 or higher) adverse event dictionary. If a subject experiences multiple events that map to a single preferred term, the greatest severity (by grade) and strongest investigator assessment of relationship to study drug will be reported for the applicable summaries.

Treatment-emergent adverse events (TEAE) are defined as events for which the date of onset is on or after the date of first dose of study drug (RSLV-132 or Placebo). Where an adverse event

(AE) collected after the date of first dose with a partially or fully missing start date or time, and it is unclear as to whether the AE is treatment emergent, it will be assumed that it is treatment emergent.

The number and percentage of subjects with adverse events will be summarized by treatment group. The percentages will be calculated based on the number of subjects in each treatment group of the SAS. System organ class (SOC) and preferred term (PT) within each SOC will be presented in descending frequency of RSLV-132 group. Subjects will be counted only once for each SOC and PT.

All adverse events (treatment-emergent and non-treatment-emergent) will be listed.

10.1.1. Overall Adverse Events

The number and percentage of subjects with at least one treatment-emergent adverse event will be summarized for the following:

- Subjects with any treatment-emergent adverse event
- Subjects with severe (Grade 3+) treatment-emergent adverse event
- Subjects with any study drug related treatment-emergent adverse event
- Any treatment-emergent adverse event leading to study drug discontinuation / study termination
- Subjects with any treatment-emergent serious adverse event
- Subjects with any study drug related treatment-emergent serious adverse event
- Subjects with outcome of death

10.1.2. Incidence of Adverse Events

Subjects with at least one treatment-emergent adverse event will be summarized by SOC, PT, and by treatment group. The incidence rate (IR) of the event per 100 patient years for each SOC and PT as well as the overall patient years of each treatment group will be calculated. IR of the event per 100 patient years will be calculated as $(\text{Total \# of Events} / \text{Patient Year}) * 100$. Patient year will be calculated as the $(\text{Total study drug exposure} / 365.25)$. Total study drug exposure will be defined as the sum of $[(\text{Last visit date} - \text{First dose date}) + 1]$.

Treatment-emergent adverse event summary by PT with descending order of frequency in the RSLV-132 group will also be presented by treatment group.

10.1.3. Relationship of Adverse Event to Study Drug

Treatment-emergent adverse events with closest relationship to study drug according to the categories specified in the protocol (Not Related, Possibly Related and Definitely Related) will be summarized for related events by SOC, PT, and treatment group.

A study drug related AE is defined as any AE that is assessed by the investigator with the relationships of “Possibly Related” and “Definitely Related”. Study drug non-related AE is defined as any AE that assessed by investigator with the relationships of “Not Related”.

Any treatment-emergent AEs that have a missing relationship will be presented in the summary table as “Related” but will be presented in the data listing with a missing relationship.

10.1.4. Severity of Adverse Event

Treatment-emergent adverse events with maximum investigator-reported severity (Grade 1-Mild, Grade 2-Moderate, Grade 3-Severe, Grade 4-Life Threatening and Grade 5-Fatal) will be summarized by SOC, PT, and treatment group.

Any treatment-emergent AEs that have a missing severity will be presented in the summary table with Toxicity Grade 4 but will be presented in the data listing with a missing severity.

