### **3.4.2 Study 132-02 Multiple Ascending Dose Study Summary: Safety**

This was a multi-center, double-blind, placebo-controlled study with successive escalating cohorts to assess the safety and tolerability of repeated IV doses (0.3 mg/kg – 10.0 mg/kg) of RSLV-132 in SLE subjects with inactive or mild disease. The MTD was not reached at the highest dose of RSLV-132 tested. Repeated administration of RSLV-132 doses was generally well tolerated by the subjects in this study. Across all dose cohorts, AEs were observed at the same overall incidence in RSLV 132 subjects as placebo subjects (6/8 subjects [75%] versus 18/24 subjects [75%]). The incidence of AEs and the average number of events per subject did not increase with increasing dose level. The most frequently reported AEs in the RSLV 132 arm were headache, nausea, and upper respiratory tract infection, each of which occurred in 5 subjects (20.8%). The majority of AEs in this study were Grade 1 in severity; 13 subjects (10 RSLV-132 and 3 placebo subjects) experienced Grade 2 AEs, and one subject in Cohort 1 of the RSLV-132 arm experienced a Grade 3 AE of acute cholecystitis (this event was also reported as the only SAE in the study). No Grade 4 or Grade 5 events occurred. Adverse events judged to be related to blinded study drug were reported for 38% of placebo subjects and 29% of RSLV 132 subjects. No dose related trends were observed for any adverse event. No deaths due to AEs occurred. All subjects had at least one out-of-range chemistry, hematology, or urinalysis value, but no values were considered clinically significant in RSLV-132 subjects. No dose-dependent trends were observed in the incidence of out-of-range values and no concerning patterns of laboratory abnormalities were detected. No notable differences between treatment groups and no trends over the course of the study were observed in vital signs or physical findings. No clinically significant ECG abnormalities were reported during the study. No confirmed positive anti-RSLV-132 antibodies were detected in any of the subjects in this 113-day study.

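### SAP 10.1.4 counts adverse events with missing severity as Grade 4, which section 10's no-imputation rule does not allow for; show them in a separate row

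*SAP*

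**What the plan says.** SAP section 10 opens the safety analyses with a general rule: "All data will be summarized as observed and no data imputation will be performed". It states no exception.

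SAP section 10.1.4 defines the severity table as "Treatment-emergent adverse events with maximum investigator-reported severity (Grade 1-Mild, Grade 2-Moderate, Grade 3-Severe, Grade 4-Life Threatening and Grade 5-Fatal"). It then says: "Any treatment-emergent AEs that have a missing severity will be presented in the summary table with Toxicity Grade 4". The same sentence treats the listing differently: the event is tabulated as Grade 4, "but will be presented in the data listing with a missing severity".

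Two other rules bear on the result:

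- **SAP 10.1:** when a subject has several events under one preferred term, "the greatest severity (by grade) and strongest investigator assessment of relationship to study drug will be reported".
- **SAP 10.1.1:** the overview table has a row for "Subjects with severe (Grade 3+) treatment-emergent adverse event". Nothing says whether a Grade 4 assigned under 10.1.4 counts in that row.

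The SAP specifies no footnote, no separate row and no sensitivity table for events without a grade.

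**The concern.** Two statements about the same data disagree. Section 10 promises observed data only. Section 10.1.4 replaces a missing grade with the highest non-fatal one. Section 10.1.4 is also at odds with its own table definition, because an assigned Grade 4 was not reported by any investigator.

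Safety and tolerability over 22 weeks is a secondary objective (SAP 2.1.2), and the trial is small. Grade 4 counts may well be zero or close to it, so a single assigned entry would be visible. A reader of the table alone could not tell it from a reported life-threatening event. Calling the rule conservative does not fully answer this: worst-case coding leans against the drug only when the event falls in the RSLV-132 arm. In the placebo arm it raises the comparator's count.

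**Working it through.** The plan gives no figure on this point, so there is none to reproduce. The check has three steps.

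**1. What the rules do to one subject.** Take a subject with two headaches recorded as Grade 1 and a third with no grade.

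| Step | Rule | Result |
|---|---|---|
| Assign a grade to the ungraded event | SAP 10.1.4 | Grade 4 |
| Keep the greatest grade for the term | SAP 10.1 | max(1, 1, 4) = Grade 4 |
| Listing | SAP 10.1.4 | Severity missing |
| Summarize as observed | SAP 10 | Grade 1, with one event ungraded |

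The table shows Grade 4, while the investigator's highest recorded grade is 1. Any recorded Grade 1 to 3 for that term would be displaced in the same way.

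**2. Size of one entry.** Inputs: about 50 subjects (SAP 2.3.7), 2:1 allocation (SAP 2.3.6), and percentages based on the subjects per arm in the Safety Analysis Set (SAP 10.1). Assumed split: 33 on RSLV-132 and 17 on placebo, all treated. Formula: k/n, with exact (Clopper-Pearson) 95% intervals.

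| Arm | No entry | One entry | Two entries, different subjects |
|---|---|---|---|
| RSLV-132, n = 33 | 0.0% (0.0 to 10.6) | 1/33 = 3.0% (0.1 to 15.8) | 2/33 = 6.1% |
| Placebo, n = 17 | 0.0% (0.0 to 19.5) | 1/17 = 5.9% (0.1 to 28.7) | 2/17 = 11.8% |

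The total enrolled matters little. With 48 subjects (32:16) one entry is 1/32 = 3.1% or 1/16 = 6.25%. With 52 (35:17) it is 1/35 = 2.9% or 1/17 = 5.9%. One placebo entry weighs 33/17 = 1.9 times as much as one RSLV-132 entry. The intervals with no entry and with one entry overlap almost entirely, so a single entry says nothing reliable about either arm's true rate.

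**3. How often it might happen.** The documents give neither an expected number of AEs nor a missing rate. Both are assumptions here, and events are treated as independent. The chance of at least one ungraded event among m events, each ungraded with probability q, is 1 − (1 − q)^m.

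| m (assumed) | q = 0.1% | q = 0.5% | q = 1% |
|---|---|---|---|
| 50 | 4.9% | 22.2% | 39.5% |
| 100 | 9.5% | 39.4% | 63.4% |
| 200 | 18.1% | 63.3% | 86.6% |

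The width of this range shows that the answer depends on q. Severity is required on the AE form (protocol 9.7), which favours the low end, and querying before lock pushes it lower still.

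**After the fix.** One ungraded event adds nothing to Grade 4. A true zero stays 0/33 or 0/17, and the event appears in its own row.

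**The case against.** The best defence is that section 10 is a general preamble and 10.1.4 a deliberate, specific rule beneath it. No programmer would be in doubt about what to do with a missing grade. The no-imputation sentence can be read as ruling out the last-observation-carried-forward method that SAP 3.2.5 applies to efficacy; SAP 10.2 repeats the ban for laboratory and other assessments. The SAP also takes the same worst-case line elsewhere: unclear onset is taken as treatment-emergent (10.1) and missing relationship as related (10.1.3). The rule is pre-specified, applies to both arms and can be traced through the listing. Much of this stands, and a reader should not infer that the two sections are impossible to reconcile. What remains is that section 10 names no exception and the table's own definition does not fit an assigned grade.

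A reader might go further and infer three things that the documents do not support:

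- **That the rule would create or hide a drug signal.** One entry is a count, no formal hypothesis testing is planned (SAP 2.3.7), and the intervals above are wide. There is also a cross-check. A life-threatening AE is serious by definition (protocol 9.2) and serious events are tabulated separately (SAP 10.1.5), so an assigned Grade 4 with no matching serious event could be recognised as an artefact.
- **That it inflates the Grade 3+ row.** Section 10.1.4 refers only to the summary table. Whether the assigned grade carries into 10.1.1 is not stated. That is a gap to close, not a demonstrated error.
- **That one assigned case would be the whole Grade 4 row.** Protocol 3.4.2 does report of the earlier multiple-dose study that "No Grade 4 or Grade 5 events occurred". But that study enrolled subjects with inactive or mild disease, 24 of them on drug, whereas this trial requires a CLASI activity score of at least 10. Its zero is a weak guide to the count here.

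**Conclusion.** The point holds as a correctable defect in the severity table. As written, an event with no grade is shown in the life-threatening row of a table defined by what investigators reported, and section 10 makes no allowance for this. One case is worth 3.0% of the RSLV-132 arm or 5.9% of the placebo arm.

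These figures assume a 33:17 split of about 50 treated subjects. The displacement of lower grades assumes that the grade is assigned before the maximum is taken; the SAP does not spell out the order, but this is the natural reading.

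The frequency is unknown and should be low. The effect is limited to a spurious, traceable count. It does not alter any efficacy result or safety-reporting duty. The correction is worth making because it is cheap and loses no information.

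**What to change.** 1. Query every missing AE severity before database lock.
2. In SAP 10.1.4, replace the Grade 4 assignment with a separate 'Missing' row, and footnote the number of such events and subjects by arm.
3. State that these events are excluded from Grade 4 and from the Grade 3+ row in 10.1.1.
4. If a worst-case view is wanted, give the Grade 4 assignment only in a labelled sensitivity table.
5. Reword section 10 to name the AE conventions that remain: unclear onset in 10.1 and missing relationship in 10.1.3.

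The cost is a few sentences of SAP text, one table row and, if wanted, one short extra table. The downside is that the main table becomes less conservative. The footnote and the sensitivity table cover that.

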10.1.5. Serious Adverse Events

All treatment-emergent serious adverse events (SAEs) will be summarized by SOC, PT, and by treatment group.

A summary of study drug related treatment-emergent SAEs by SOC, PT, and treatment group will also be presented.

10.1.6. Adverse Events Leading to Hospitalization / Study Drug Discontinuation / Study Termination

All treatment-emergent adverse events that lead to either required or prolonged inpatient hospitalization or study drug discontinuation or study termination will be summarized by SOC, PT, and by treatment group.

10.2. Laboratory and Other Safety Assessments

Each assessment will be summarized descriptively by treatment groups on the SAS. For assessments not measured at Baseline (Day 1) pre-dose, Screening Visit value will be used as the baseline. No missing data imputation will be used.

All data will be listed.

10.2.1. Laboratory Blood and Urine Samples

Laboratory hematology, serum chemistry and urinalysis samples will be collected for each subject at scheduled visits for safety evaluations. The laboratory test parameters are listed in the Protocol Appendix B. The samples are analyzed by a central laboratory.

Observed values and the change from Baseline (Day 1) at each visit will be summarized for the continuous values. Number and percentage of subjects in each category will be summarized for the categorical values. In addition, the number and percentage of subjects who have the lab results that are noted to be “Clinically Significant” by the investigator will be summarized. The percentages will be calculated based on the actual number of subjects at each visit in each treatment group of the SAS. Grade 3 or higher lab toxicity (based on Rheumatology CTC Grade System) during the study will also be summarized.

Serum and urine pregnancy tests are for women of childbearing potential only. Serum pregnancy test will be performed at Screening Visit and Day 215 (EOS). The samples are analyzed by a central laboratory. The urine pregnancy test will be done at Baseline (Day 1) only and will be performed at each study site. Serum and urine pregnancy test data will be listed only.

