### 6.3 Subject Exclusion Criteria

The following will exclude potential subjects from the study:

1. severe, active CNS involvement at Screening;

2. severe renal involvement (urine protein/creatinine ratio of >200 mg/mmol, or an estimated creatinine clearance of <30 mL/min) at Screening;
3. use of cyclophosphamide within 3 months of Baseline;
4. use of background medications within 1 month of Baseline in excess of:
  - a. mycophenolate mofetil > 3 g/day;
  - b. azathioprine > 200 mg/day;
  - c. methotrexate > 25 mg/week;
  - d. hydroxychloroquine > 400 mg/day;
  - e. prednisone (or equivalent) > 15 mg/day;
5. use of an intravenous corticosteroid “pulse” within 2 months of Baseline;
6. use of an intramuscular steroid injection within 1 month of Baseline;
7. use of rituximab within 6 months of Baseline;
8. use of belimumab within 3 months of Baseline;
9. acute infection or history of acute infection within seven days prior to Baseline;
10. positive viral load test for hepatitis B, C or HIV at Screening;
11. receipt of an investigational product within 3 months of Baseline or five half-lives (whichever is longer);
12. positive pregnancy test at Screening or at Baseline;
13. female subjects currently breast feeding at Baseline;
14. inability or unwillingness to comply with study restrictions, return for follow up appointments, or other considerations, in the opinion of the Investigator, which would make the candidate unsuitable for study participation.

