### **9.9 Abnormal Test Findings**

When laboratory results are outside the normal range, a decision regarding whether the result is of clinical significance or not shall be made by the Investigator and shall be based, in part, upon

the nature and degree of the observed abnormality. Abnormal evaluations may be repeated, to rule out lab error.

The criteria for determining whether an abnormal objective test finding should be reported as an AE are as follows:

- Test result is associated with accompanying symptoms, and/or;
- Test result requires additional diagnostic testing or medical/surgical intervention, and/or;
- Test result is considered to be an AE by the investigator or Sponsor.

An abnormal test result, in the absence of any of the above conditions, does not constitute an AE.

Any abnormal test result that is determined to be an error does not require reporting as an AE.

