## 17 APPENDICES

### 17.1 Appendix A: Study Procedures

Study Procedures	Screen (-28 to -1)	Baseline Day 1	Day 8	Day 15	Day 29	Day 43	Day 57	Day 71	Day 85	Day 99	Day 113	Day 127	Day 141	Day 155	Day 169 (EOT)	Day 215 (EOS)
Acceptable Visit Window (days)			$\pm 3$	$\pm 5$	$\pm 5$											
Informed Consent	X															
Inclusion/exclusion	X	X a														
Demographics	X															
Weight, height	X															
Hepatitis, HIV tests	X															
Physical exam	X	X b			X b	X b										
Pregnancy tests	X c	X d														X c
AE assessment		X	X	X	X	X	X	X	X	X	X	X	X	X	X	X
Medical/medication history	X	X e	X e	X e	X e	X e	X e	X e	X e	X e	X e	X e	X e	X e	X e	X e
Vital signs	X	X	X	X	X	X	X	X	X	X	X	X	X	X	X	X
Chem-20, CBC, UA	X	X			X		X		X		X		X		X	X
SLEDAI, BILAG, PGA, joint count		X			X		X		X		X		X		X	
CLASI	X	X			X		X		X	X	X	X	X	X	X	
Photographs of cutaneous disease	X	X							X						X	

Study Procedures	Screen (-28 to -1)	Baseline Day 1	Day 8	Day 15	Day 29	Day 43	Day 57	Day 71	Day 85	Day 99	Day 113	Day 127	Day 141	Day 155	Day 169 (EOT)	Day 215 (EOS)
Acceptable Visit Window (days)			+3	+3	+3	+3	+3	+3	+3	+3	+3	+3	+3	+3	+5	+5
FACIT index		X							X						X	
Serum for study drug concentration		X			X				X						X	X
Serum for protein analysis		X							X						X	
Serum for RNase activity		X			X				X						X	X
Whole blood for gene expression		X			X				X						X	X
Serum for autoantibody, C3, C4 profile	X	X			X		X		X		X		X		X	
Serum for ADA		X		X	X				X							X
Study Drug administration		X f	X	X f												

a CLASI activity and damage score and confirm no changes in SLE medications only

b directed physical exam

c serum pregnancy test for women of childbearing potential (7.4)

d urine pregnancy test for women of childbearing potential (7.4)

e interim medical/medication history only

f RSLV-132 or placebo shall be administered according to the infusion rate and time set forth in the Study Drug Reference Manual

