3.2.8. Visit Windows

The case report form nominal visits and visit windows will be used in the summaries. In general, unscheduled visits will not be summarized unless otherwise noted.

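### The Grade 3+ laboratory summary has no baseline reference, so persisting pre-dose abnormalities count as toxicity, and it may leave out results seen only on unscheduled samples

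*SAP*

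**What the plan says.** SAP 10.2.1 opens with "Laboratory hematology, serum chemistry and urinalysis samples will be collected for each subject at scheduled visits for safety evaluations". It plans observed values and change from Baseline by visit for continuous parameters, counts for categorical ones, and a count of results that the investigator marks as clinically significant. It then adds that "Grade 3 or higher lab toxicity (based on Rheumatology CTC Grade System) during the study will also be summarized". That sentence does not mention the Baseline grade, worsening or worst grade. It does not say whether Screening and Day 1 values count, or whether unscheduled samples do.

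Three other places bear on it:

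- SAP 3.2.8 sets a general default: "In general, unscheduled visits will not be summarized unless otherwise noted".
- SAP 10.2 does define a laboratory baseline: "For assessments not measured at Baseline (Day 1) pre-dose, Screening Visit value will be used as the baseline". In 10.2.1 this is used only for change in continuous values.
- Protocol 9.9 foresees off-schedule tests: "Abnormal evaluations may be repeated, to rule out lab error".

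The schedule in Protocol Appendix A reads "Chem-20, CBC, UA X X X X X X X X X". With Protocol 12.5 and 12.6, the marks correspond to Screening, Baseline and Days 29, 57, 85, 113, 141, 169 and 215.

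**The concern.** A toxicity count is meant to show what arose or got worse after dosing. Without a baseline reference, a subject who enters with a Grade 3+ value and keeps it is counted alongside a subject who develops one on treatment. Restricting the count to post-dose samples would not cure this, because the persisting value appears in those samples too.

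Abnormal hematology at entry is plausible here. Protocol 6.3 sets no hematology limit, and Protocol Appendix D lists hemolytic anemia, leukopenia, lymphopenia and thrombocytopenia among the qualifying SLE criteria.

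The second difficulty is which samples count. If the 3.2.8 default governs the Grade 3+ table, an abnormality that appears and resolves between scheduled draws, and is seen only on an unscheduled sample, is missing from it.

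At stake is the one planned summary that compares graded laboratory toxicity between arms. SAP section 4 plans no interim analysis or data monitoring committee, so the final tables are the only planned aggregate comparison.

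**Working it through.** The plan states no figure on this point and has no power calculation (SAP 2.3.7), so there is nothing to reproduce. The check is of the text, followed by illustrations whose assumptions are marked.

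**1. How the SAP treats comparable safety outputs**

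| Output | Reference to the pre-dose state |
|---|---|
| Adverse events (SAP 10.1) | Treatment-emergent, defined by onset relative to first dose |
| Physical exam (SAP 10.2.4) | New, unchanged, worsened or improved against Baseline |
| Continuous laboratory values (SAP 10.2.1) | Change from Baseline |
| Grade 3+ laboratory toxicity (SAP 10.2.1) | None stated |

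The Grade 3+ summary is the exception, although the baseline value it needs is already defined in SAP 10.2.

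**2. Weight of one subject.** Inputs are about 50 subjects and 2:1 allocation (SAP 2.3.7 and 2.3.6).

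- 50 × 2/3 = 33.3, about 33 on RSLV-132; 50 × 1/3 = 16.7, about 17 on placebo.
- One subject is 1/33 = 3.0 points or 1/17 = 5.9 points.
- Example: one new and two persisting cases on RSLV-132 give 3/33 = 9.1% as written, against 1/33 = 3.0% counting only the new case.

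**3. Chance that the baseline problem arises at all.** The prevalence p of any Grade 3+ laboratory value at baseline is an assumption. The chance of at least one such subject in an arm of n is 1 − (1 − p)^n.

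| Assumed p | Expected, n = 33 | Chance of ≥1, n = 33 | Expected, n = 17 | Chance of ≥1, n = 17 |
|---|---|---|---|---|
| 2% | 0.7 | 49% | 0.3 | 29% |
| 5% | 1.7 | 82% | 0.9 | 58% |
| 10% | 3.3 | 97% | 1.7 | 83% |

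These subjects enter the count only if the abnormality persists or, should the table include pre-dose samples, regardless.

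**4. What scheduled draws alone would see.** There are seven post-baseline draws. The gaps from Day 1 are 28 days six times, then 215 − 169 = 46 days. The first draw, on Day 29, follows three infusions (Days 1, 8 and 15).

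Assume an abnormality lasts d days, starts on any day from Day 2 with equal chance, and ends by Day 215. There are 215 − d possible starts. Of these, 6d + 1 overlap a scheduled draw (d for each of the first six, one for Day 215), for d up to 28. The number falling wholly between draws is (215 − d) − (6d + 1) = 214 − 7d.

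| Assumed duration d | Between draws / possible starts | Share |
|---|---|---|
| 7 days | 165/208 | 79% |
| 14 days | 116/201 | 58% |
| 21 days | 67/194 | 35% |
| 28 days | 18/187 | 10% |

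These shares describe what the schedule can miss. The default in 3.2.8 matters only for the part of them that an unscheduled sample does catch, and that part is not known.

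**The case against.** **The sample rule is ambiguous.** A reader might infer that the SAP definitely excludes unscheduled results from this table. The text does not go that far. SAP 3.2.8 sits under visit windows, is worded as a general rule, and allows exceptions. Within 10.2.1 other laboratory summaries are tied to each visit, while the Grade 3+ sentence refers to the whole study, which can fairly be taken as the exception. That stands. It also means two defensible programs would give two different tables.

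**Ill subjects do not vanish.** Under Protocol 9.1 and 9.9, an abnormal result with symptoms, or one needing further testing or intervention, is reported as an adverse event. It is graded on the same Rheumatology CTC scale (Protocol 9.7), and SAP 10.1.1 and 10.1.4 tabulate Grade 3+ events and maximum severity. Results marked clinically significant are summarized, and all data are listed. This also stands, and it limits the consequence. It does not replace a laboratory grade comparison. Adverse event reporting depends on the criteria above or on judgement, and Protocol 9.1 prefers a diagnosis to the abnormal value. The clinically significant count has no grade, and listings do not compare arms.

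**Baseline Grade 3+ values are not shown to exist.** A reader might infer them from the renal limit in Protocol 6.3, "severe renal involvement (urine protein/creatinine ratio of >200 mg/mmol, or an estimated creatinine clearance of <30 mL/min) at Screening", or from the out-of-range values that Protocol 3.4.2 reports in the earlier SLE study. Neither supports it. The Rheumatology CTC cut-offs are not in the documents, so values just inside the renal limits cannot be graded, and creatinine clearance is not among the parameters in Protocol Appendix B. Out of range is not Grade 3, and Protocol 3.4.2 reports no clinically significant value on RSLV-132 in a population with inactive or mild disease. Nor does a qualifying cytopenia in Appendix D imply Grade 3. It makes baseline abnormality plausible, no more.

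**The analysis is descriptive.** No formal testing is planned (SAP section 5), so no error rate is at issue. The table is nevertheless meant to be read across arms.

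**Conclusion.** The point holds in two parts of unequal strength. The missing baseline reference is plain on the text: as written, a persisting pre-dose Grade 3+ value is counted as toxicity. The omission of unscheduled results is what the 3.2.8 default produces unless 10.2.1 is read as an exception, so it is an ambiguity to settle and not a demonstrated omission.

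The between-arm table can partly reflect baseline differences. A reader might infer that it would simply measure chance imbalance at baseline, but that would need pre-existing cases to dominate, and no count in the documents supports it. The number of affected subjects is unknown. The firm figures are the weight of one subject in each arm and the spacing of scheduled draws. The other percentages rest on assumed prevalence (2% to 10%), assumed duration (7 to 28 days) and uniform onset.

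This is more than missing detail, because the SAP already applies a better rule to adverse events and physical examination.

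**What to change.** Amend SAP 10.2.1, naming it as an exception to 3.2.8:

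- The Grade 3+ summary uses every result in the database after the first dose, scheduled or unscheduled, except documented laboratory error.
- A subject counts for a parameter only if the worst post-dose grade is 3 or higher and is worse than the Baseline grade, with Baseline as defined in SAP 10.2.
- A shift table gives Baseline grade against worst post-dose grade for each parameter by arm. It keeps subjects with a persisting Grade 3+ value visible without counting them as new toxicity.

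The rule should be settled before unblinding, so that the choice of which results count is not made with treatment known.

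The cost is a few SAP sentences, minor programming and one more table. No visit, sample or aspect of subject management changes. One limit remains: the documents do not say whether unscheduled or local results are captured, so they can be used only where they are in the database and can be graded. The report should say so.
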